### 7.2.13 Word Recognition Score (WRS)

The WRS in quiet assesses the ability to repeat phonemically balanced single syllable words unknown to the subject. The words are presented at 35-40dB SL or at Most Comfortable Level (MCL), as determined by the examiner, via insert earphones or headphones in the sound booth. The recorded list of NU-6 words (Northwestern University Auditory Test No. 6) are presented to each ear separately, and the subject is asked to repeat the words. The number of correct and incorrect responses are documented as a percentage for each ear.

### 7.2.14 Tinnitus Reaction Questionnaire (TRQ)

The TRQ is a self-reported scale designed to assess the psychological distress associated with tinnitus. The scale records tinnitus-related effects on lifestyle and general well-being. Specifically, the 26-item scale covers general distress, interference with work and leisure activities, signs of severe distress, and avoidance of activities. The subject rates each item on a 5-point scale according to the degree of applicability.

### 7.2.15 Speech, Spatial, and Qualities of Hearing Scale (SSQ)

The SSQ was developed to assess listeners' subjective sense of listening ability and listening experience in everyday complex situations that often involve spatial hearing. The 49-item self-assessment of hearing measures the ability/disability in a variety of complex listening situations typical of those encountered in everyday life. The subject will complete the response to each question and the answers will be scored by the Investigator.

### 7.2.16 QuickSIN-EP

The QuickSIN™ (Etymotic Research) is a speech-in-noise test that quickly and easily measures the ability to hear in noise. The Quick SIN includes a total of 18 unique 6-sentence lists composed of Institute of Electrical and Electronics Engineers (IEEE) sentences, which were designed to provide limited contextual cues to aid in understanding. The sentences are spoken by a female talker and are presented at a constant level in a background of 4-talker babble (one male and three females). The background noise is considered most representative of the noise encountered in

typical social situations. The babble level in each list decreases in intensity in 5 dB steps from +25 to 0 dB in order to vary the signal-to-noise ratio (SNR) (Killion et al., 2004). The test provides an assessment of the subject's ability to understand speech in noise as a SNR rather than as a percent correct score. For the purposes of this study, the QuickSIN performed with insert earphones will be referred as QuickSIN-EP.

The subject is asked to repeat the sentences presented by insert earphones in the sound booth, and each sentence has 5 key words. Each correctly repeated word is awarded one point for a possible score of 30 points per list. The score is determined by the use of the formula 25.5 - Total Words Correct = SNR loss. The SNR loss score, calculated for each ear separately, represents the SNR a listener with hearing loss requires above the SNR a normal hearing listener requires to achieve 50% correct sentence identification (Killion, 1997). The test will be conducted according to the most current manual and version.

The QuickSIN will also administered by sound field (see Section 7.2.18 below) to assess binaural speech-in-noise performance.

#### 7.2.17 Words-in-Noise (WIN)

The Words-in-Noise test evaluates the ability of a listener to understand words in the setting of multi-talker babble background. The level of the multi-talker background is fixed and the stimulus words are presented at seven signal-to-noise ratios from 24 to 0dB in 4 dB decrements. The word lists are based on the Northwestern University Auditory Test No. 6 (Tillman and Carhart, 1966) and spoken by a female speaker. The monosyllabic words are pre-recorded with a noisy background. The test is administered using insert earphones in the sound booth and is conducted in each ear separately. The test assesses the signal-to-noise ratio for each ear at which recognition performance is 50% according to the Spearman-Karber equation (Wilson et al., 2007).

#### 7.2.18 Sound Field Speech Test: QuickSIN-SF

Sound-field (free-field) Speech testing signals are presented via a single front speaker at a 0° azimuth to the subject's face who is positioned in the center of the room. The QuickSIN test content will be used to assess speech detection in the setting of background multi-talker babble, allowing binaural measurement of speech-in-noise performance in the sound field. For the purposes of this study, the QuickSIN performed in the sound field will be referred as QuickSIN-SF.

#### 7.2.19 Pure Tone Audiometry

The pure tone audiogram measures the subject's hearing ability by frequency (pitch) and intensity (volume) by both air and bone conduction. The audiogram determines the degree, type, and configuration of hearing loss. The test assesses air and bone conduction thresholds for each ear over frequencies from 250Hz to 8000Hz (note, bone conduction is not measured at 250 or 8000Hz). Extended high frequency hearing from 10000Hz to 16000Hz will also be assessed, if available based on site audiometer specifications. To reduce ambient noise, pure-tone audiometry will be performed in a sound booth connected to an external audiometer with insert earphones up to 8000Hz and circumaural headphones for frequencies above 8000Hz. The insert earphones are

small transducers which fit into the ear canal and further reduce ambient noise and crossover of auditory stimuli to the non-test ear.

The audiometry, using pulsed tone stimulus, will be performed according to standards as outlined by the modified Hughson Westlake procedure as per ANSI standards (ANSI S3.21-1978 [R-1982]). Pure tone air and bone conduction threshold audiometry may be measured with and without masking. Effective masking levels should be recorded. An audiometer instrument/device typical to audiology clinics, including high frequency capabilities when available, will be used to present pulsed pure tones and determine thresholds. For thresholds of frequencies between 0.25 and 8 kHz (0.25, 0.5, 1, 2, 3, 4, 6, and 8 kHz) insert earphones (ER-3A) will be placed into the ear canal. To determine ultra-high frequency thresholds at 10, 11.2, 12.5, 14, 15, and 16 kHz, circumaural earphones will be used, if available based on site audiometer specifications. A modified Hughson-Westlake procedure will be used to determine thresholds at each frequency using a down 10 dB, up 5 dB step size for intensity and where threshold is the lowest pulsed tone intensity that the subject responds at 50% accuracy in at least 2/3 trials.

Documentation confirming the annual standardized calibration of the audiometer, earphones, and speakers will be required.

#### **7.2.20 Distortion Product Otoacoustic Emission (DPOAE)**

The DPOAEs are an objective indicator of normally functioning cochlear outer hair cells. DPOAE are generated by the OHCs as they expand and contract in response to two simultaneous tones of different frequency. The test does not require a response from the subject, and a sound booth is not required.

Subjects will be fitted with a soft flexible probe, consisting of a sensitive microphone and transducers, which will create a seal when inserted into the ear canal. DPOAEs will be tested in at least 4 frequencies with a single stimulus level and varying frequency. To be considered a present DPOAE, the noise floor will be assessed to determine if it is low enough to evaluate the responses and the difference between the response and the noise floor at each frequency will exceed 5 dB.

Documentation confirming the annual standardized device calibration will be required.

#### **7.2.21 Auditory Brainstem Response (ABR)**

ABR audiometry is a neurologic test of auditory brainstem function in response to brief auditory (e.g., click or tone-burst) stimuli. Auditory evoked potentials are extracted from underlying brainstem electrical activity and recorded by electrodes placed on the scalp or in the ear-canal with the subject in the sound booth or a quiet room.

The normal response to the 2-4 kHz click stimulus presented at high intensities (e.g., 70-90 dB normalized hearing level [nHL]) consists of a series of neutrally-generated waveforms within 10 milliseconds of the auditory stimulus by tip-trode. Waves I-III are generated by the auditory branch of the eighth cranial nerve, and Wave IV-V is generated by the upper brainstem. The ABR waveforms will be assessed by amplitude (microvoltage), latency (milliseconds), interpeak latency, and interaural latency.

The ABR Wave I response is a far-field representation of the compound auditory nerve action potential (AP) in the distal portion of the 8th cranial nerve and is hypothesized to arise from the dendrites of the auditory nerve. It has been suggested that ABR Wave I amplitude, as well as the summing potential (SP)-to-AP ratio and speech recognition in noise, offers an effective nonbehavioral measure of CS (Barbee et al., 2018). Transducer calibration will be documented at each site.

#### 7.2.22 Electrocochleography (ECochG)

ECochG is similar to ABR in that electrical potentials are measured in response to sound stimulation but is recorded using a non-invasive extra-tympanic electrode placed in the ear canal (i.e., tip-trode). The three potentials generated by ECochG include the cochlear microphonic, the SP and AP. The SP:AP ratio is considered possibly related to the status of the cochlear synapse.

The ECochG will be conducted as a component of the ABR. The ipsilateral electrode will be paired with the contralateral, or reference, electrode in the non-test ear. The forehead or nasion will be used as the ground electrode. Impedance should be less than 5000 ohms, but may be higher for the ipsilateral electrode. The transducer signal will consist of a click at 90 dB nHL, and the test will be repeated until a reliable waveform is observed. Transducer calibration will be documented ■ each site.

## 8. ADVERSE AND SERIOUS ADVERSE EVENTS ASSESSMENT

### 8.1 Definition of Adverse Events, Period of Observation, Recording of Adverse Events

An *Adverse Event* (AE) is any untoward medical occurrence in a clinical investigation subject administered a pharmaceutical product and that does not necessarily have a causal relationship with this treatment. An AE can therefore be any unfavorable and unintended sign (including an abnormal laboratory finding), symptom, or disease temporally associated with the use of a medicinal (investigational) product, whether or not related to the medicinal (investigational) product (ICH Guidance E2A,1995).

All AEs should be captured on the AE CRF.

All AEs are collected from the time the informed consent is signed until the final visit is completed at approximately 90 days post-injection. All AEs are to be recorded on the appropriate AE pages in the CRF and in source documents. Where possible, a diagnosis, rather than a list of symptoms, should be recorded. If a diagnosis has not been made, then each symptom should be listed individually. In addition to untoward AEs, unexpected benefits outside the IP indication should also be captured on the AE CRF.

All AEs must be followed to closure (the subject's health has returned to his/her baseline status or all variables have returned to normal), an outcome is reached, stabilization (the Investigator does not expect any further improvement or worsening of the event), or the event is otherwise explained regardless of whether the subject is still participating in the study. When appropriate, medical tests and examinations are performed so that resolution of event(s) can be documented.

#### 8.1.1 Severity Categorization

The severity of AEs must be recorded during the course of the event including the start and stop dates for each change in severity. An event that changes in severity should be captured as a new event. Worsening of pre-treatment events, after initiation of IP, must be recorded as new AEs (for example, if a subject experiences mild intermittent dyspepsia prior to dosing of IP, but the dyspepsia becomes severe and more frequent after first dose of IP has been administered, a new AE of severe dyspepsia [with the appropriate date of onset] is recorded on the appropriate CRF). The medical assessment of severity is determined by using the definitions provided in Table 4:

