## 2.2 Endpoints

### 2.2.1 Primary Endpoint

The primary endpoint of the study is the number and severity of AEs up to 3 months following a single unilateral intratympanic injection of PIPE-505.

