## 9.8 Safety Analyses

AEs will be coded using the most current version of Medical Dictionary for Regulatory Activities (MedDRA) as of the start of the study. The number of events, incidence, and percentage of treatment-emergent adverse events (TEAE) will be calculated overall, by system organ class (SOC), and by preferred term. Events with missing onset dates will be included as treatment-emergent. Treatment emergent events are considered those events with onset dates on or after

study drug exposure or events with dates of onset or worsening after study drug exposure. If a subject experiences more than one occurrence of the same AE, the occurrence with the greatest severity and the closest association with the study drug will be summarized. TEAEs will be further summarized by severity and relationship to IP. AEs related to IP, AEs leading to withdrawal, SAEs, and deaths will be summarized/listed.

Clinical laboratory tests, vital signs, and ECG findings will be summarized by treatment group and visit. Change from baseline values will be summarized using shift tables. Potentially clinically important findings will also be summarized or listed.

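### Does the protocol leave open whether the number of AEs counts severity changes or episodes, and whether a pre-dose event that eases becomes treatment-emergent?

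*Protocol*

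**What the plan says.** The primary endpoint (Protocol Section 2.2.1) is "the number and severity of AEs up to 3 months following a single unilateral intratympanic injection". Events enter the database early: Section 8.1 states that "All AEs are collected from the time the informed consent is signed until the final visit is completed", and Section 7.1.1 allows screening within 56 days of randomization.

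Section 8.1.1 sets the recording rules. It requires start and stop dates for every change in severity, and then says "An event that changes in severity should be captured as a new event". The next sentence deals with events already present before dosing: "Worsening of pre-treatment events, after initiation of IP, must be recorded as new AEs".

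Section 9.8 sets the analysis: "The number of events, incidence, and percentage of treatment-emergent adverse events (TEAE) will be calculated overall", and also by system organ class and preferred term. The definition of treatment emergence has two limbs. It opens "Treatment emergent events are considered those events with onset dates on or after" and continues "study drug exposure or events with dates of onset or worsening after study drug exposure". Where a subject has the same AE more than once, "the occurrence with the greatest severity and the closest association with the study drug will be summarized".

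Section 9.3 leaves detailed statistical definitions to the SAP and gives the SAP precedence. The SAP contents list Section 10.2, Adverse Events. The public copy of the SAP passes from Section 3.9 to the later indexes, so the body of Section 10.2 cannot be read.

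**The concern.** Two readings of the visible text lead to different tallies of a quantity named in the primary endpoint.

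- **Counting unit.** Section 8.1.1 first treats severity as something tracked within one event, then makes each change a new event. Section 9.8 reports a number of events and does not say whether the split records are joined first.
- **Pre-dose events that ease.** The general sentence in 8.1.1 gives no direction of change. A pre-dose event that drops a grade after injection could be given a new record with a post-dose start date, and the first limb of the treatment-emergent definition asks only for such an onset date.

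If nothing else settled these points, two programmers could produce different event counts from the same data. With six placebo subjects, a single reclassified subject would be visible in a percentage. If severity changes were recorded more often in one arm, the comparison of counts would be distorted as well.

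**Working it through.** The documents state no figure on this point, so there is none to reproduce. The check sets the recording rules against the analysis rules and counts assumed histories under each reading.

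**Inputs from the documents.** 18 active and 6 placebo subjects (Protocol Section 3.1); the rules in Sections 8.1.1 and 9.8. The frequency of severity changes is not given anywhere.

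**Step 1. Three assumed histories.** These are illustrations, not trial data.

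| History | Records, any post-dose onset | Records, worsening only | Episodes, any post-dose onset | Episodes, worsening only |
|---|---|---|---|---|
| A: post-dose mild, moderate, mild | 3 | 3 | 1 | 1 |
| B: pre-dose moderate, easing to mild after dosing | 1 | 0 | 1 | 0 |
| C: pre-dose mild, becoming severe after dosing | 1 | 1 | 1 | 1 |
| Total | 5 | 4 | 3 | 2 |

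The ambiguity can therefore change a tally.

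**Step 2. Size of the tally effect.** With c the mean number of severity changes per post-dose episode, records per episode = 1 + c.

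- c = 0 gives 1.0; c = 0.5 gives 1.5; c = 1 gives 2.0; c = 2 gives 3.0.
- The active-to-placebo ratio of counts is multiplied by (1 + c_active)/(1 + c_placebo), which equals 1 when c is the same in both arms.

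These values of c are assumptions, so the range shows what is arithmetically possible and is not an estimate.

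**Step 3. What record splitting does not touch.** History A is one subject with one AE whose worst grade is moderate, whether it is held as three records or one. The greatest-severity rule in Section 9.8 returns that same row. Subject incidence and maximum severity for post-dose episodes are the same under either counting unit.

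**Step 4. Size of the easing effect.** An eased pre-dose event classed as treatment-emergent adds at most one subject to incidence:

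- active: 1/18 = 5.6 percentage points, moving active minus placebo by +5.6;
- placebo: 1/6 = 16.7 percentage points, moving the difference by -16.7.

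Overall incidence moves only if that subject has no other treatment-emergent event. Section 1.3.1 expects injection-related events such as ear pain, dizziness and ear fullness, so many subjects may already be counted.

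**Step 5. Which reading the visible text favours for easing.** The one sentence in 8.1.1 written for pre-treatment events names worsening, and so does the second limb in 9.8. Counting an eased event requires the general sentence to override the specific one that follows it.

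**Step 6. Whether a decision depends on it.** The two event-based suspension criteria in Section 3.4 are triggered by numbers of subjects. Section 9.8 describes no hypothesis test on AEs, and the sample size has no statistical basis (Section 9.12).

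**The case for a change.** The strongest case for acting is that the number of AEs is named in the primary endpoint and its unit is not defined in the visible text. The greatest-severity rule does not supply one. If it governed the event count, the count for each preferred term would equal the number of subjects and repeat the incidence column. The injecting otologist knows the treatment, and Section 6.3.2 lets that person assess AEs, so how often a severity change is recorded is not fully protected by the blind. Settling the unit would cost only a few words. Even if SAP Section 10.2 already does so, sites record events from the protocol.

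Part of this stands. Protocol Sections 8.1.1 and 9.8 alone do not define the unit, and the first limb of the treatment-emergent definition does not expressly exclude easing. The rest is weaker. Differential recording between arms is possible but not shown. The protocol also has a coherent literal reading, in which each captured record is one event and each subject is summarized at worst grade; counting by episode is another convention, and nothing in the documents makes it the correct one. Site recording needs no change, because the dates required for each severity change allow either count to be derived afterwards.

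**Conclusion.** The wording is loose, but this is a detail that analysts settle in the ordinary course, and no change to the plan follows. The unit of an event count and the derivation of treatment emergence are definitions that Protocol Section 9.3 assigns to the SAP, and the SAP section on adverse events is withheld from the public copy. Its absence there is not evidence that the plan lacks the rule, nor can it be assumed that the rule is there. At most, a reader with access to SAP Section 10.2 would confirm that it states the counting unit and limits treatment emergence of pre-dose events to worsening.

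The tally multiplier is 1 + c with c unknown, and the between-arm ratio is undistorted if c is equal in the two arms. Per misclassified subject, incidence moves by at most 5.6 points (active) or 16.7 points (placebo). That needs an event that began before dosing, was still present at Day 0 and then dropped a grade without resolving, in subjects required to be in general good health, with the general sentence in 8.1.1 read against the specific one beside it. Worst severity and subject incidence for post-dose episodes and the event-based suspension criteria are unaffected. The conclusion rests on the severity-change dates being collected as 8.1.1 requires, so that with about 24 subjects episodes can be rebuilt from the data.

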**Table 4: Adverse Event Severity**

Severity	Description
Mild	A type of AE that is usually transient and may require only minimal treatment or therapeutic intervention. The event does not generally interfere with usual activities of daily living.
Moderate	A type of AE that is usually alleviated with specific therapeutic intervention. The event interferes with usual activities of daily living, causing discomfort but poses no significant or permanent risk of harm to the research subject.
Severe	A type of AE that interrupts usual activities of daily living, or significantly affects clinical status, or may require intensive therapeutic intervention.

### 8.1.2 Relationship Categorization

The Investigator, whether blinded or unblinded (i.e., the otologist or neuro-otologist performing the intratympanic injection), must evaluate the potential relationship to “Study Drug” for each AE, wherein “Study Drug” will include both Placebo and PIPE-505 Suspension. Therefore, the Investigator should attribute causation to the Study Drug if the AE is most consistent with an effect secondary to injection of a substance, either Placebo or PIPE-505 Suspension, into the tympanic space. If there is no valid reason for suggesting a relationship, then the AE should be classified as ‘not related’. Otherwise, if there is any valid reason, even if undetermined or untested, for suspecting a possible cause-and-effect relationship between the ‘Study Drug’ and the occurrence of the AE, then the AE should be considered ‘related’. The causality assessment in relation to Study Drug (without recording any unblinding information) must be documented in the source document and graded according to Table 5 below. The AE patterns specific to treatment assignment (subjects who received active PIPE-505 Suspension versus Placebo) will ultimately be determined upon final analysis of the unmasked database at study conclusion.

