As noted above, no human data with PIPE-505 has been collected, but nonclinical studies indicate that restoration of the cochlear synapse and generation of new OHCs could improve auditory function in subjects with SNHL with speech-in-noise impairment (secondary to suspected CS). The physiology and function of the human cochlear synapse indicates that the therapeutic effect of PIPE-505, and thereby preliminary efficacy (refer to exploratory objectives and endpoints), could include improved signal-to-noise processing. This treatment effect will be detected by improved performance from baseline on the QuickSIN and/or the WIN, specific speech-in-noise measures that test the ability of the subject to hear speech or words in the setting of competing background noise. Other hearing measures that could reflect evidence of preliminary efficacy include the Word Recognition Score (WRS), Speech Recognition Threshold (SRT), and Speech Special Qualities (SSQ). Improved cochlear synaptic function may also be detected by electrophysiological changes in the ABR, electrocochleography (ECochG), and/or the Middle Ear Muscle Reflex (MEMR). Finally, the treatment effect, potentially related more to OHC regeneration, could also be reflected in changes from baseline in pure tone audiometry and distortion product otoacoustic emission (DPOAE).

Given the local, and unilateral, administration of PIPE-505 directly into the tympanic cavity as a single dose, a favorable systemic safety profile is anticipated. Expected adverse events (AEs) are likely to be related to the effects of intratympanic injection and have been observed in other studies involving the same route-of-administration (Meyer, 2013; Staecker et al., 2017). The more common otologic/audiologic responses associated with tympanic injection may include transient vertigo, ear pain, dizziness, nausea, ear fullness or transient reduction in hearing. The expected AEs related to this study and PIPE-505 are fully summarized in the IB.

The dose of PIPE-505 in this study is based on the NOAEL established in nonclinical studies (as summarized above) and the relevant Human Equivalent Dose (HED) conversion derived from the allometric difference in perilymph volume from the guinea pig to the human. A ten-fold safety factor (HED/10) is then applied to the HED to calculate the Maximum Recommended Safe Dose (MRSD). Based on the nonclinical studies (summarized in the IB), the MRSD calculated for this

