## 6.3 Administration of Investigational Product(s)

### 6.3.1 Index Ear Selection and Dosing Procedure

The IP or Placebo will be administered by an intratympanic injection as an out-patient procedure by a qualified otologist or neuro-otologist. The ear selected for dosing (i.e., the Index Ear) will be identified based on the audiometry and QuickSIN results at Screening as follows:

- The ear with the worse audiometry, as determined by the PI, will be identified as the Index Ear.
- If both ears are equal by audiometry, the ear with the highest SNR on the QuickSIN will be defined as the Index Ear.
- If the audiometry and QuickSIN are equal in each ear, the PI and subject will determine the Index Ear.

Otoscopy of the Index Ear canal and TM will be performed prior to administration and excessive earwax or debris will be manually cleared. At the discretion of the otologist or neuro-otologist performing the intra-tympanic injection, a topical anesthetic (e.g., EMLA cream [eutectic lidocaine/prilocaine mixture] or xylocaine [4% lidocaine solution or 10% pump spray]) may be applied to the external tympanic membrane. Given the transient discomfort associated with topical anesthesia and the extremely small gauge of the needle used for injection, the Investigator may also elect to perform the intra-tympanic injection without use of a topical anesthetic, after discussion with the subject. If applied, any remaining anesthetic in the external canal will be suctioned off prior to the injection in order to avoid spillage into the tympanic cavity and possible vertigo or dizziness. Any local anesthetic, if utilized, should be recorded in the subject's source record and the Concomitant Medications case report form.

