**Table 5: Adverse Event Causality Assessment**

Term	Relationship	Definition
Related	Yes	The temporal relationship between the event and the administration of the investigational product is compelling and/or follows a known or suspected response pattern to that product, and the event cannot be explained by the subject’s medical condition, other therapies, or accident.
Not Related	No	The event can be readily explained by other factors such as the subject’s underlying medical condition, concomitant therapy, or accident and no plausible temporal or biologic relationship exists between the investigational product and the event.

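### The text of Protocol Section 8.1.2 grades every adverse event as related or not related, but Table 5, which it makes binding, has no row for some of them

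*Protocol*

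**What the plan says.** Section 8.1.2 asks the Investigator, blinded or not, to judge the relationship of each AE to Study Drug, a term it defines to include both Placebo and PIPE-505. It gives a two-way rule:

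- Not related: "If there is no valid reason for suggesting a relationship, then the AE should be classified as" not related.
- Related: in all other cases, "if there is any valid reason, even if undetermined or untested, for suspecting a possible cause-and-effect relationship" to Study Drug.

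The paragraph then says that the causality assessment "must be documented in the source document and graded according to Table 5 below". Table 5 has two rows:

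- Related: the timing is compelling and/or the event "follows a known or suspected response pattern to that product, and the event cannot be explained by" the subject's condition, other treatments or an accident.
- Not Related: the event has a ready alternative cause, for example an "underlying medical condition, concomitant therapy, or accident and no plausible temporal or biologic relationship exists between the investigational product and the event".

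There is no third row, and nothing states whether the text or the table takes precedence.

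**The concern.** The two rules apply to the same assessment but set different conditions. Under the text, a competing explanation does not stop an AE from being related. Under Table 5 it does, yet the AE cannot move to Not Related while a plausible relationship remains. An Investigator who must choose a row could choose either, so two sites could grade the same event differently.

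Relatedness is used in three places:

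- The AE summaries by relatedness (Synopsis, statistical analyses; Section 9.8).
- The choice of which repeat occurrence of an AE is summarized (Section 9.8).
- The notification of SAEs that are both related and unexpected (Section 8.2.7).

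The groups are small, with 18 active and 6 placebo subjects planned. One subject moved between categories changes a subject-level percentage by 1/6 = 16.7 points on placebo or 1/18 = 5.6 points on PIPE-505.

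**Working it through.** The plan states no figure to reproduce. The check sets the two definitions side by side.

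**Coarse grid.** Take two yes/no questions: is there a plausible link to Study Drug, and is there another explanation? A valid reason to suspect a link (text) is treated as the same thing as a plausible relationship (Table 5).

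| Plausible link | Other explanation | Text of 8.1.2 | Table 5 |
|---|---|---|---|
| Yes | No | Related | Related, if timing is compelling or the response pattern is known or suspected |
| Yes | Yes | Related | No row |
| No | Yes | Not related | Not Related, if readily explained |
| No | No | Not related | No row |

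The text covers 4 of 4 combinations and Table 5 at most 2 of 4. Of the two without a row, the text makes one related and one not related.

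**Finer grid.** Table 5 uses graded terms, so split the link into none, plausible only, and strong (compelling timing or a response pattern). Split the other explanation into none, possible, and ready. This gives 3 × 3 = 9 cells:

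- Strong link, no other explanation: related by both.
- No link, ready explanation: not related by both.
- Plausible or strong link, with a possible or ready explanation (2 × 2 = 4 cells): related by the text, no row.
- Plausible-only link, no other explanation (1 cell): related by the text, no row.
- No link, with no explanation or one that is possible but not ready (2 cells): not related by the text, no row.

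Table 5 classifies 2 of 9 cells; 4 + 1 + 2 = 7 have no row. In no cell does it give the opposite label to the text.

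**Can the gap be reached?** Two routes follow from the protocol:

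- *Vertigo or dizziness.* Section 1.3.1 says that responses to tympanic injection "may include transient vertigo, ear pain, dizziness, nausea, ear fullness or transient reduction in hearing". Section 6.3.1 has leftover topical anesthetic suctioned off "in order to avoid spillage into the tympanic cavity and possible vertigo or dizziness", so the anesthetic is a second possible cause. If used, it is entered in the subject's "source record and the Concomitant Medications case report form", which makes it one of Table 5's other therapies. It is optional and the residue is removed, so this concerns only some subjects.
- *Reduced hearing.* It is among the injection responses in Section 1.3.1, and Section 8.1.4 also names it as a symptom of the disease under study. Every subject has bilateral sensorineural loss (inclusion criterion 4). Significant worsening must be recorded as an AE, and after injection it may have both a plausible link and an explanation in the underlying condition.

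**The case against.** The strongest reply is that this is a gap and not a contradiction in outcome. The text is a complete rule, and Table 5 can be read as merely supplying the Yes/No grade to record. An Investigator who finds no matching row still has an instruction in the same paragraph. That reading is possible, but Table 5 is headed with definitions and the paragraph says to grade by it, so the stricter reading is equally open.

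Section 8.1.2 also tells the Investigator to attribute an event to Study Drug when an injection effect is the most consistent explanation, which would direct much post-injection vertigo to related. This does not close the gap. Such an event can still have another explanation, which fails the Related row, and the sentence adds a third standard to the two already there.

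The anesthetic example is narrow, since it needs the anesthetic to be used and some to remain and spill. That stands; the hearing example does not depend on it.

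The limits on the consequences also stand. The primary endpoint counts AEs and their severity (Section 2.2.1). Investigators report SAEs whatever the relationship (Sections 8.2.3 and 8.2.4). Section 8.1.2 leaves the treatment comparison to the unmasked data. The suspension rules in Section 3.4 use their own wording on relatedness. With only two grades, the rule for choosing an occurrence adds little. The AE text of SAP Section 10.2 is not in the public copy, so any analysis convention there cannot be checked. Such a convention would not change what the site recorded.

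**Conclusion.** The inconsistency is real and should be corrected. Table 5 covers at most 2 of the 4 basic combinations that the text covers, and 2 of 9 on the finer grid. These counts depend on how the graded terms are split, and on equating a valid reason with a plausible relationship. The core case, a plausible link together with another explanation, has no row under either split. The effect is confined to relatedness grading and its uses, chiefly the descriptive summaries and the notification of related, unexpected SAEs. The documents give no AE rates, so the number of events affected is unknown.

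**What to change.** Reconcile Section 8.1.2 and Table 5 on one exhaustive two-category definition. The simplest way is to rewrite Table 5 to match the text:

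- **Related:** there is any valid reason, proven or not, to suspect a relationship to Study Drug.
- **Not Related:** there is no valid reason to suspect one.

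Use the term Study Drug in Table 5 as well. The table now refers to the investigational product, which the abbreviations list equates with PIPE-505 and Section 6.3.1 names separately from Placebo, while the text of 8.1.2 includes both.

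The cost is a wording change to one table, with no added visits, CRF fields or analyses. The downside is that more AEs may be graded related than under a strict reading of the present table. A sponsor that prefers to keep an alternative-explanation condition could do so, provided the text and table then agree and every AE has a row.
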